### **5.2.1 Assessments**

The following data will be collected from subjects during the follow-up phone call:

- Impact of Events Scale
- Procedure Preference and Acceptability Questionnaire
- Adverse event assessment
- Follow-Up Case Report Form (eCRF): This captures relevant information for questionnaire completion and assessment of adverse events.

### **5.2.2 Impact of Events Scale**

The impact of events scale will be completed with the subject during the follow-up phone call and measures subjective distress related to administration of the Cytosponge.

### **5.2.3 Procedure Preference and Acceptability Questionnaire**

The procedure preference and acceptability questionnaire will be completed with the subject during the follow-up phone call. This assessment collects subject preference for the Cytosponge or traditional upper endoscopy as well as willingness to undergo the procedure again.

### **5.2.4 Follow-up Phone Call Adverse Event Assessment**

During the follow-up phone call, subjects should be assessed for any adverse events that have occurred since administration of the Cytosponge. Only those events that are potentially related to participation in this research study must be reported. See section 7.2 for the definition of a reportable adverse event. Sites are responsible for following local IRB/EC guidelines for reporting adverse events to their local IRB/EC.

## **5.3 Repeat Cytosponge Administration**

If the initial Cytosponge sample is inadequate, sites will be notified and subjects will be asked to return for repeat Cytosponge administration 30 days (+/- 10 days) after the initial Cytosponge administration. Only the Cytosponge administration will be repeated. Questionnaires and the endoscopy procedure will not be repeated on these patients. See section 5.1.3 for details on the Cytosponge administration procedure. The Repeat Administration eCRF should be completed.

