#### 1.3.1 Prior Utilization

[name] and colleagues administered Cytosponge to 504 patients in a primary care setting and found it to be safe and well-tolerated. Of these patients, 501 (99%) were able to successfully swallow the capsule. Unsurprisingly, given pill-swallowing difficulty in the general population, 3 patients were unable to swallow

the pill, feeling it was too large. No adverse events were noted, and patients demonstrated a low level of anxiety associated with the test. These 504 administrations are documented in a report in the British Medical Journal. These investigators have, since this investigation, administered the Cytosponge to an additional 831 patients as part of the BEST2 study (a multicenter, prospective study to determine whether BE patients can be risk stratified using the Cytosponge) and an interim data analysis shows similarly excellent safety and tolerance profile, with no adverse events reported. Overall, to date, there have been 1,335 documented administrations of the sponge, with no adverse events. Several hundred additional uses of the device have occurred in Cambridge, UK, without adverse event (personal communication, [name]), but have not yet been reported in the peer-reviewed literature.

Cytosponge is extremely similar to Cytosponge I. Although no complications have been reported with this device, there are several theoretical risks associated with the administration of this device. There is the possibility of aspiration whenever instrumentation of the esophagus or stomach is performed. Because the device does not render the upper esophageal sphincter incompetent, this risk is expected to be minimal. Additionally, although the sponge is soft and non-abrasive, subjects could bleed from any mucosal surfaces of the mouth, stomach or esophagus which come in contact with it, and/or experience a sore or irritated throat following administration. Finally, to date there have been >1,000 administrations and detachment of the sponge from the string has occurred in less than 1% of cases. Should the sponge detach from the string, it will be retrieved during the routine care upper endoscopy immediately following administration.

The current study has been designed to minimize occurrence of these theoretical risks. Specifically we plan to exclude those patients who:

- Are unable to discontinue clopidogrel, and/or warfarin for 7 days prior and 7 days after procedure,

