- Have a history of esophageal stricture,
- Have any history of esophageal varices, liver impairment of moderate or worse severity (Child's-Pugh class B & C), or evidence of varices noted on any past endoscopy,
- Have any history of esophageal surgery (except uncomplicated fundoplication), and history of coagulopathy, with INR >1.3 and/or platelet count of <75,000.

Importantly, all patients enrolled in this study will have previously and recently received an upper endoscopy during which absence of findings putting the subject at higher risk for these theoretical concerns (conditions such as varices and stricture) will be documented.

Cytosponge administration will occur after an overnight fast to minimize the possibility of aspiration of any gastric contents. Every administered sponge will be assessed post-procedure for signs of fracture or incomplete retrieval of the sponge. In the unlikely case of incomplete retrieval, the sponge will be retrieved with a Roth net at the standard of care endoscopy which will routinely immediately follow the administration of the sponge per the study protocol. Any bleeding noted, either clinically following the sponge administration or due to blood on the sponge itself, will be similarly investigated, and, as necessary, treated during the subsequent endoscopy. Because study inclusion/exclusion criteria are designed to exclude those at highest risk for a bleeding complication, the risk of bleeding in this study should be extremely low.

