## 3 Study Design

### 3.1 General Design

This is cross-sectional study of subjects with dysplastic BE who have undergone successful endoscopic ablation with RFA, to assess the utility of the Cytosponge assay as a non-endoscopic method for monitoring the post-ablation patient. In addition, we will enroll a small cohort of up to 50 subjects with a current diagnosis of BE to collect pilot data for a larger scale study. Subjects presenting to UNC Hospitals for routine endoscopic examinations for current BE or after successful ablation will be offered enrollment in the study. After informed consent, and the same day as the endoscopic procedure, the subject will undergo administration of the Cytosponge assay. The patient will then undergo routine endoscopic surveillance, using a standard Seattle biopsy surveillance protocol. The Cytosponge will be placed in fixative and shipped to the [name] laboratory for processing according to their established protocols. Tissue biopsies will undergo standard processing and H&E staining, with assessment by expert gastrointestinal pathologists at UNC. The primary outcome variables will be sensitivity and specificity of the novel assay, compared against the gold standard of the presence of recurrent BE as detected by upper endoscopy with biopsies. Secondary outcomes include acceptability of the nonendoscopic assay to the patient (assessed by a standardized tool, the Impact of Events Scale, as well as a visual analogue scale), and likelihood of assay positivity as a function of amount of residual disease (as measured by Prague criteria).

[figure not shown]
If the initial administration of the Cytosponge demonstrates an inadequate sample, defined as a sample that does not demonstrate at least one columnar cell on hematoxylin & eosin staining, repeat Cytosponge administration will be performed at 30 days (+/- 10 days) from the initial administration.

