### **4.2 Exclusion Criteria**

1. Current use of blood thinners such as coumadin, warfarin, clopidogrel, heparin and/or low molecular weight heparin (requires discontinuation of medication 7 days prior to and 7 days after esophagogastroduodenoscopy [EGD] and Cytosponge administration, aspirin use is OK).
2. Known bleeding disorder
3. For the post-RFA cohort, prior ablative therapy of the esophagus other than radiofrequency ablation (RFA), including photodynamic therapy (PDT), more than one session of spray cryotherapy, and any other ablation therapies is exclusionary. However, prior endoscopic mucosal resection (EMR) is acceptable and up to two prior treatments of thermal/coagulation therapy (other than RFA) for focal residual disease following otherwise successful RFA therapy is acceptable. The BE cohort must be treatment naive and have no history of ablation, but prior EMR is acceptable.
4. History of esophageal stricture precluding passage of the endoscope or sponge,
5. Pregnancy, or planned pregnancy during the course of the study,
6. Any history of esophageal varices, liver impairment of moderate or worse severity (Child's- Pugh class B & C) or evidence of varices noted on any past endoscopy,
7. Any history of esophageal surgery, except for uncomplicated fundoplication, and,
8. History of coagulopathy, with INR>1.3 and/or platelet count of <75,000.
9. Planned ablation therapy within 3 days of Cytosponge administration (endoscopic mucosal resection and submucosal dissection is OK).

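### Repeat Cytosponges (day 20-40) lack the same-day endoscopy that section 1.3.1 relies on for rescue, and no contact is scheduled after them

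*Combined protocol and SAP*

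**What the plan says.** **Rescue.** Section 1.3.1 gives one remedy for each device hazard.
- Detachment: "Should the sponge detach from the string, it will be retrieved during the routine care upper endoscopy immediately following administration".
- Incomplete retrieval: "the sponge will be retrieved with a Roth net at the standard of care endoscopy which will routinely immediately follow the administration".
- Bleeding, whether clinical or seen on the sponge: it "will be similarly investigated, and, as necessary, treated during the subsequent endoscopy".

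The same section requires inspection: "Every administered sponge will be assessed post-procedure for signs of fracture or incomplete retrieval of the sponge".

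**Repeats.** A subject whose first sample is inadequate returns for a second sponge 30 days (+/- 10) after the first. Section 5.3 adds: "Questionnaires and the endoscopy procedure will not be repeated on these patients". The Study Summary and footnote 1 of the schedule in section 5 also exclude endoscopy at the repeat. For procedure, 5.3 refers to 5.1.3, which describes swallowing, withdrawal, fixation and failure to swallow, and otherwise defers to the device's instructions for use.

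**Follow-up.** Section 5.2 sets one call 7 days (+/- 2) after the Cytosponge and endoscopy. Sections 4.4 and 5.2 treat the subject as finished once that call is made. The repeat visit is the last column of the schedule, with only the sponge and adverse events marked.

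**Blood thinners.** Exclusion 1 in section 4.2 "requires discontinuation of medication 7 days prior to and 7 days after esophagogastroduodenoscopy [EGD] and Cytosponge administration". The schedule marks the eligibility check at enrollment only.

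**The concern.** The risk section justifies giving the device partly because an endoscopist will be at work in the same subject minutes later. That is true of the first sponge and untrue of the second. Anyone who judges the trial's risk from 1.3.1 would believe that every administration has this cover.

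Follow-up is uneven in the same direction. The first sponge is followed by an endoscopic look at the mucosa and a call a week later. The same device given again has neither, and it is given to someone whom the protocol has already classed as having completed the study. The stakes are subject safety and the completeness of safety data after repeats. Sample size and the acceptability endpoints are not affected.

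**Working it through.** The main point needs no rate. It follows from reading the sections side by side and from simple day counts.

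**1. Safeguard against schedule**

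| Element | First sponge (day 0) | Repeat sponge |
|---|---|---|
| Sponge inspected afterwards (1.3.1) | Yes | Yes |
| Endoscopy straight afterwards | Yes | No (Study Summary, section 5 footnote 1, 5.3) |
| Named route for retrieval or bleeding | That endoscopy (1.3.1) | None in 5.3 or 5.1.3 |
| Adverse events assessed at the visit | Yes | Yes |
| Scheduled contact afterwards | Call, day 5-9 | None |
| Eligibility check marked in schedule | Yes | No |

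**2. Timing** (windows from sections 5, 5.2 and 5.3)
- Repeat: 30 - 10 = day 20 to 30 + 10 = day 40.
- Call: 7 - 2 = day 5 to 7 + 2 = day 9.
- Gap from call to repeat: shortest 20 - 9 = 11 days, longest 40 - 5 = 35 days. The call always comes before the repeat.
- Blood thinners may restart after day 7, which is 20 - 7 = 13 to 40 - 7 = 33 days before a repeat.
- The same call placed after a repeat: 20 + 5 = day 25 to 40 + 9 = day 49.

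**3. Scale (illustration only)**

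The documents give no rate of inadequate samples, so 1% to 20% is assumed. N = 374 is the planned enrollment (324 post-ablation plus 50 BE). Section 1.3.1 says only that detachment is below 1%, so 1% is a ceiling.

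Repeats = 374 x rate. Expected detachments at the ceiling = repeats x 0.01.

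| Assumed inadequate | Repeats without endoscopy | Expected detachments, at most |
|---|---|---|
| 1% | 3.7 | 0.04 |
| 5% | 18.7 | 0.19 |
| 10% | 37.4 | 0.37 |
| 20% | 74.8 | 0.75 |

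Even at the top of the range, fewer than one detachment is expected. If the true detachment rate were 0.1%, also an assumption, the expected number would be a tenth of these figures.

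**The case against.** The best case for the plan is that the risk is small and that other provisions surround it. The device is cleared and used within its labeling. Section 1.3.1 reports no adverse events in 1,335 administrations. Each repeat subject had an endoscopy 20 to 40 days earlier, the single center has an endoscopy unit, and nothing forbids a clinically indicated endoscopy. The instructions for use, the site data and safety-monitoring plan required by section 7.3, or the consent pages may name a pathway. None of these was available for this review, nor were the design figure and protocol map. All of this stands, and it limits the claim to the visible text. It does not make 1.3.1 true for repeats, and it does not supply a contact afterwards.

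A reader might infer more than the documents support:
- **That a detachment at a repeat would be missed.** No: every sponge is inspected. What is missing is the stated remedy.
- **That a delayed event would come to light only through the subject.** Too strong. Adverse events are assessed at the repeat visit, section 7.2.2 requires questioning at each contact, and section 7.1 obliges the investigator to notify the sponsor of related post-study events. The gap is that no later contact is scheduled.
- **That the plan allows a repeat on blood thinners.** No: exclusion 1 refers to Cytosponge administration, and a repeat is one. Only a prompt in the schedule is missing.
- **That a detachment is about as likely as not.** The formula 1 - 0.99^75 gives 53%, but it combines an assumed 20% inadequacy with a ceiling used as the rate. At 0.1% the same 75 repeats give 1 - 0.999^75 = 7%.
- **That the adverse event reporting period must be rewritten.** It runs 30 days from completion of a biomarker panel that the text does not define. If that means the assay on the adequate sample, it already extends past the repeat.
- **That accuracy would be noticeably biased.** A repeat result may be compared with a day-0 endoscopy after which treatment was given. The size depends on inputs that the plan does not state. If 2% of recurrent cases had a repeat, 25% of those were treated in between, and 8% stayed positive (1 minus the quoted 92% specificity), sensitivity would move from 87.0% to 0.87 - 0.02 x 0.25 x (0.87 - 0.08) = 86.6%. An inadequate sample is "defined as a sample that does not demonstrate at least one columnar cell", so inadequacy should be rarer still in recurrent disease. This does not carry a finding.

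**Conclusion.** The point holds in two parts. First, the same-day endoscopic safeguard in 1.3.1 does not exist for repeat sponges at day 20-40, and the visible text offers no substitute. Second, the only call precedes any repeat by 11 to 35 days and closes participation, so no contact is scheduled after the last device exposure. Neither part rests on an assumed rate.

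The practical size is small. Detachment is quoted as below 1%, no adverse events were reported in 1,335 uses, and the number of repeats is unknown. The documents do not support reading this as a likely harm, as a repeat permitted on anticoagulants, or as a threat to the accuracy estimates. It is worth correcting because a safety statement is wrong for some subjects and the remedy costs little. An on-demand pathway in the unseen material would settle the practical side of the first part, but 1.3.1 would still need the qualification.

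**What to change.** 1. In 4.4, 5.2, 5.3 and the schedule: add the existing 7-day (+/- 2) call, adverse events only, after a repeat sponge (day 25-49). Define the end of participation as the call after the last sponge.
2. In 1.3.1 and 5.3: state that same-day endoscopic rescue does not cover repeats. State also that detachment, incomplete retrieval or bleeding at a repeat is handled by on-demand referral to the endoscopy unit, with repeats done while that unit is open.
3. As a minor clarification, in 5.3 and the schedule: confirm the exclusion 1 washout (7 days before and 7 days after) at the repeat visit.

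**Cost.** Protocol wording, one short call per repeat subject (about 4 to 75 calls at the assumed 1% to 20%), one washout check at the repeat visit, and a minor limit on when repeats can be booked. On-demand referral would add fewer than one expected endoscopy for detachment across that range, plus any for bleeding. Standby endoscopy and routine repeat endoscopy are not needed. Sample size and analysis are unchanged.

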# **6 Statistical Plan**

## **6.1 Sample Size Determination**

Previous data suggest a sensitivity of Cytosponge analysis for detecting BE ranging from 84-90%, and a specificity of 92-94%, using upper endoscopy as a gold standard. It is unlikely that this technique will be appropriate for surveillance if the true sensitivity is much lower than 80%, given the unacceptably high rate of false negatives. Previous data document a rate of recurrent BE of 13-38% in subjects assessed with surveillance endoscopy. If we wish to assess the accuracy of the Cytosponge compared to upper endoscopy, assuming a baseline sensitivity of 87%, we will need to enroll 81 subjects with recurrent BE to

yield a 95% confidence interval of 10% or less. If we further assume a rate of recurrent BE of 25% in the post-ablation population, a total of 324 post-ablation subjects will need to be enrolled in the trial.

## 6.2 Statistical Methods

For the primary objective, to assess the acceptability of the novel mucosal sampling technique in subjects after successful ablation, we will assess the distribution of Impact of Events Scale scores, and the intrusiveness and avoidance subscales. We will generate measures of central tendency and distribution of these data. Bivariate analysis will be performed to assess for predictors of low tolerance of Cytosponge surveillance, and a logistic regression model created to assess these factors while controlling for potential confounders. Data will be compared to population norms using parametric statistics. VAS scores will be calculated, and measures of central tendency and distribution reported.

Subjects' preferences for Cytosponge vs. endoscopic surveillance, as well as willingness to undergo the procedure again, will be measured as proportions, with bivariate and multivariate analyses for predictors of preference performed.

For the secondary objective, to assess the operating characteristics of Cytosponge against a gold standard of upper endoscopy, initially 2x2 tables will be constructed demonstrating Cytosponge and the gold standard findings (Y/N for BE). Sensitivity, specificity, positive predictive value, negative predictive value and accuracy will be calculated. Because Cytosponge positivity may vary based on the burden of BE, we will perform sensitivity analyses, defining "positive" cases as those with recurrent BE of  $\geq 1$  cm in length, and then  $\geq 2$  cm in length, to assess impact of disease burden on operating characteristics. Multivariate models controlling for age, sex, period of time from last ablation, burden of residual disease, and other potential confounders will be constructed, to assess the impact of these factors on test accuracy. Although we do not expect to see an association between the degree of dysplasia and Cytosponge positivity, exploratory analyses will be performed using degree of dysplasia as a predictor variable, and Cytosponge positivity as the outcome variable.

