## 2 Study Objectives

### *Primary objective:*

To assess the acceptability of a novel, minimally invasive esophageal mucosal sampling technique, the Cytosponge, in subjects undergoing surveillance after radiofrequency ablation. Based on previous data, we hypothesize that the sponge-based sampling technique will be associated with low levels of patient distress, and will be preferred by patients, when compared to standard sedated upper endoscopy, for surveillance of their esophageal mucosa.

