Subject recruitment will be from consecutive eligible patients presenting for routine care surveillance endoscopy of current BE or following endoscopic ablation of BE. Potentially eligible subjects will be contacted by telephone in advance of their procedure and their interest in study participation assessed. Subjects interested in participating will be asked to present to the endoscopy unit one hour prior to their scheduled procedure. At that time, inclusion and exclusion criteria will be reviewed, and eligible subjects will give informed consent. Subjects will then undergo the Cytosponge assay. Following Cytosponge assay, subjects will complete the procedure acceptability measures described below. Subjects will then attend their usual surveillance endoscopy session. Upper endoscopy will be performed and biopsies taken as part of routine care. Importantly, no record of the results of the standard endoscopy and biopsies will be provided to those assessing the Cytosponge results and these individuals will be masked to all clinical data. Similarly, the pathologists interpreting the histological specimens from the endoscopy will have no knowledge of the outcomes of the Cytosponge assay. Only the study biostatistician will have access to these data.

Primary assessment of acceptability will be via the Impact of Events Scale. This widely used scale was developed to assess the distress associated with a specific life event. It includes measures of both the intrusiveness of the event, and any avoidance responses by the subject in response to the event. Final scores are between 0-75, with low scores demonstrating a low impact of the event. The scale will be administered 7 days after the sampling in order to allow the subjects to have time to reflect on the experience and to compare with the EGD. Secondary acceptability outcomes will include a visual analogue scale of acceptability of the Cytosponge, performed after the Cytosponge is administered. Also, the subject will be asked whether he/she would be willing to repeat the assay, and, assuming similar accuracy between Cytosponge and upper endoscopy, whether he/she would rather undergo surveillance by Cytosponge or standard EGD with biopsies.

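### The predictor model for poor tolerance has no defined outcome; cutting a 0–75 score in two loses power, heavily if few subjects fall in the poor-tolerance class, and an open cut inflates false positives

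*Combined protocol and SAP*

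**What the plan says.** Section 3.1 gives the IES the leading role for acceptability: "Primary assessment of acceptability will be via the Impact of Events Scale". It is a numeric scale: "Final scores are between 0-75, with low scores demonstrating a low impact of the event". Section 3.1 then adds other measures: "Secondary acceptability outcomes will include a visual analogue scale of acceptability of the Cytosponge", plus willingness to repeat the test and preference between the two procedures.

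Section 6.2, repeated in the Study Summary, starts from the whole score: "we will assess the distribution of Impact of Events Scale scores, and the intrusiveness and avoidance subscales". It then turns to "predictors of low tolerance of Cytosponge surveillance", using bivariate analysis and "a logistic regression model created to assess these factors while controlling for potential confounders". The bivariate test is not named. Neither document section says which scale defines low tolerance, where the cut lies, or where a cut would come from. No effect size, power or expected class size is given for this analysis.

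The hypothesis in Section 2 is that "the sponge-based sampling technique will be associated with low levels of patient distress".

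**The concern.** Ordinary logistic regression needs a two-class outcome, and the plan does not define one. Two things follow.

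First, the scale and cut can be settled after the scores are known. A cut picked because it gives an interesting result can produce a predictor that is not real.

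Second, the method makes poor use of data already collected. If distress is low, as hypothesised, a cut high enough to mean poor tolerance will isolate few subjects, and a multivariable model adjusted for confounders will rest on few events. A larger class is available only by cutting among low scores, where the label stops meaning much.

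At stake is the only planned multivariable analysis of the IES, the one that would show which patients tolerate the device badly.

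**Working it through.** **Is there a figure to reproduce?** Not for this analysis. The only sample size is in Section 6.1: "a total of 324 post-ablation subjects will need to be enrolled in the trial". It comes from 81 subjects with recurrent disease divided by a 25% recurrence rate, 81/0.25 = 324, and is driven by the precision of sensitivity. It fixes the number available here but carries no power statement about acceptability.

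**Inputs.** From the documents: N = 324, and a 0–75 score with low values expected. Assumed: a two-level predictor split 162/162, two-sided 5% tests, a normal latent score, and an effect giving 80% power on the uncut score.

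**Step 1, effect size.** d = (1.960 + 0.842) × √(2/162) = 2.802 × 0.1111 = 0.311 SD.

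**Step 2, power after a cut.** Choose c so that the overall share above it is q: ½[1 − Φ(c)] + ½[1 − Φ(c − d)] = q. This gives group shares p₁ and p₂. Then

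power = Φ{ [(p₂ − p₁) − 1.96·√(2q(1 − q)/162)] / √([p₁(1 − p₁) + p₂(1 − p₂)]/162) }.

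For q = 10%: p₁ = 0.073 and p₂ = 0.127; the null standard error is √(2 × 0.10 × 0.90/162) = 0.0333, and the other is 0.0332. So Φ{(0.0536 − 0.0653)/0.0332} = Φ(−0.35) = 36%.

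**Step 3, information kept.** Relative efficiency = φ(z_q)²/[q(1 − q)], multiplied by 324 for an effective N.

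| Share classed low-tolerance | Events | p₁, p₂ | Power (80% uncut) | Power (90% uncut, d = 0.360) | Efficiency | Effective N |
|---|---|---|---|---|---|---|
| 50% | 162 | 0.438, 0.562 | 61% | 73% | 0.64 | 206 |
| 20% | 65 | 0.157, 0.243 | 49% | 61% | 0.49 | 159 |
| 10% | 32 | 0.073, 0.127 | 36% | 46% | 0.34 | 111 |
| 5% | 16 | 0.034, 0.066 | 25% | 32% | 0.22 | 73 |

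By the usual ten-events-per-predictor guide, 32 events support about three predictors and 16 support one or two.

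**Step 4, a skewed score.** Simulation with assumed scores (47% zeros, mean about 4.5, 162 v 162, common odds ratio 2.0) gave about 90% power for a rank test on the whole score. After a cut, power was 69% with about 65 events, 28% with about 18 and 9% with about 9.

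**Step 5, free choice of cut.** Independent tests would give 1 − 0.95³ = 14.3% for three cuts and 1 − 0.95⁵ = 22.6% for five. Cuts of one score are correlated, so simulation is needed. Taking the smallest p-value with no true effect gave about 9–13% for three cuts and 14–17% for five. These values move by a point or two with the spacing of the cuts and the test used.

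**The case against.** **The IES may not be what is cut.** Section 6.2 does not say so. The visual analogue scale could define tolerance, as could unwillingness to repeat, which is already yes/no. This stands: the IES reading is an inference. It rests on the sentence following directly on the IES sentences and coming before the other measures are introduced. If another measure was meant, the scale is open as well as the cut, so the gap in prespecification is wider.

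**The loss is not always large.** A reader might infer that the plan throws away most of its power. The documents do not support that, because they give no mean, spread or class share. With 20–50% classed low-tolerance, 49–61% power remains out of 80%. More than half the power goes only at about 10% or fewer. In another set of skewed-score simulations (assumed mean of 6 or 10 points in the lower group), cuts at 9 to 30 points gave 46–57% power against 59–61% for a rank test, a small gap at the best cuts.

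**An ordered model is not always better.** The figures favouring it assume that the predictor acts across the scale. When 10% of one group was instead moved to 20–44 points, the rank test had about 36% power against 81% for a cut at 20. This also stands: poor tolerance may be a question about the tail, so a prespecified cut deserves a place.

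**It is a supporting analysis.** The hypotheses of low distress and of preference for the sponge do not depend on this model. That limits the weight of the point but does not remove it.

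**Conclusion.** The point holds in limited form. The outcome of the predictor model is undefined in scale and cut-off, and nothing in the plan stops either being chosen after the scores are seen. That alone roughly doubles or triples the 5% error per predictor when three to five cuts are tried.

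Dichotomising also costs power when an effect spreads over the score: from 80% to about 61% at a median cut and to 25% with 5% in the class. These figures rest on an assumed normal latent score, an evenly split predictor and an assumed class share. The low-distress hypothesis makes a small class plausible; it does not establish one.

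A reader might also infer that the acceptability assessment as a whole is undermined. It is not: the distribution and central tendency of the IES and its subscales are reported uncut. The weakness is confined to the predictor analysis. It should be corrected, but does not threaten the study's main conclusions.

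**What to change.** In Section 6.2 and the Study Summary:

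- Make the main predictor analysis a proportional-odds model of the IES total and of each subscale, on the same predictors and confounders, with rank-based tests for the bivariate step.
- Keep the logistic model as a secondary analysis only. Name one scale and one cut-off, with the reason for it, before any scores are seen.
- Limit the predictors in that secondary model to what the expected number of events can support.

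Adding a cut-off alone would stop the post hoc choice but leave the loss of power.

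The cost is wording: no new data, subjects or visits. The downside is that the main odds ratio is averaged over the whole scale, and the ordered model is less sensitive to a predictor that acts only on marked distress. That is why the prespecified cut is kept as secondary.
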